3.1.2 Efficacy-Evaluable Analysis Set

The Efficacy-Evaluable Analysis Set includes all subjects received at least 1 dose of FPA150, had at least 1 postbaseline evaluable tumor assessment unless death or clinical progressive disease occurred prior to the first post baseline disease assessment.

The Efficacy-Evaluable Analysis Set will be used in the summary of efficacy data.

3.1.3 DLT-Evaluable Analysis Set

The DLT-Evaluable Analysis Set includes all enrolled subjects in Phase 1 monotherapy and in combination with pembrolizumab who received at least 2 doses of FPA150, and completed Cycles 1 of treatment, or who experienced a DLT in Cycle 1.

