4.1.2.2 Definition of a Dose-Limiting Toxicity

4.1.2.2.1 FPA150 Monotherapy

DLTs during Phase 1a Dose Escalation are defined as any of the following events regardless of attribution (except for those events clearly due to the underlying disease or extraneous causes):

- Any Grade 3 or higher non-hematologic toxicity (except Grade 3 nausea, vomiting and diarrhea) occurring with the first 21 days of treatment
- Grade 3 nausea, vomiting, diarrhea lasting > 72 hours, despite optimal supportive care, occurring within first 21 days of treatment
- Febrile neutropenia and/or documented infection with absolute neutrophil count (ANC) < 1.0×10^9 per L, Grade 4 neutropenia lasting more than 7 days, Grade 4 thrombocytopenia (< 25.0×10^9 per L), or Grade 3 thrombocytopenia (< $50.0-25.0 \times 10^9$ per L) accompanied by bleeding within first 21 days of treatment
- Aspartate aminotransferase/alanine transaminase (AST/ALT) > 3 × upper limit of normal (ULN) and concurrent total bilirubin > 2 × ULN not related to liver involvement with cancer
- Other Grade 3 laboratory values that are not of clinical significance according to Investigator and Sponsor agreement that do not resolve within 72 hours
- Any Grade 4 laboratory value regardless of clinical sequelae

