9.2 Populations for Analyses

The following analysis populations are defined for the study:

- Safety Population—all patients who have received any portion of at least one dose of FPA150.
- DLT-Evaluable Population—all patients enrolled into Phase 1 monotherapy and in combination with pembrolizumab who received at least two doses of FPA150 and completed Cycle 1 of treatment, or who experienced a DLT in Cycle 1.
- Pharmacokinetic Full Analysis Population: All patients who received at least one dose of FPA150 and had at least one FPA150 serum concentration result.
- Pharmacokinetic -Evaluable Population—all patients in the PK Full Analysis Population who had sufficient PK sample for the calculation of at least one PK parameter on at least one Study Day.
- Efficacy-Evaluable Population—all patients who met eligibility criteria, received at least one dose of FPA150, have measurable tumor lesions at baseline, and have at least one post-baseline disease assessment unless the death and clinical progressive disease occurred prior to the first post baseline disease assessment.

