1.1.2 Study Design: Phase 1a Dose Exploration

Phase 1a includes a dose exploration cohort that may enroll beyond 3 patients (up to

20 additional patients across all dose levels). These 20 patients include 10 patients whose tumors express high levels of B7-H4 protein (3 mg and 10 mg), to further evaluate safety, PK, pharmacodynamics, and clinical activity at that dose (to be conditional upon the dose level clearing DLT criteria) of FPA150 monotherapy. It also includes up to 10 patients selected to have varying levels of B7-H4 expression [REDACTED] [REDACTED] dosed at the FPA150 monotherapy MTD/RD.

Table 3: Proposed Dose Cohort/Level for Phase 1a Dose Exploration

Cohort	Dose/Regimen	B7-H4 Status
1aE1	FPA150 3 mg/kg	High
1aE2	FPA150 10mg/kg	High
1aE3	FPA150 monotherapy MTD/RD	[REDACTED]

Abbreviations: MTD = maximum tolerated dose; Q3W = once every 3 weeks; RD = recommended dose

Toxicities observed in these patients will contribute to the overall assessment of safety and tolerability, but will not be included in the formal DLT calculations per Protocol.

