3.2 Subject Grouping

Subjects will be grouped according to the actual treatment they received. Subjects with the same dose level from the dose escalation and exploratory in Phase 1a for monotherapy and safety lead-in in Phase 1a and Phase 1b for combination will be combined for summary.

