7.1.7 Dose-Limiting Toxicity

The summary and listing of DLTs will be performed on the DLT-Evaluable Analysis Set. A summary of DLT will be provided by SOC, PT, and severity. All DLTs will be listed.

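### The DLT-Evaluable set is not limited to Dose Escalation and the Combination Safety Lead-in, so the reported DLT denominator can include patients in whom DLTs were never formally assessed

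*SAP*

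**What the plan says.** **The set.** SAP 3.1.3: "The DLT-Evaluable Analysis Set includes all enrolled subjects in Phase 1 monotherapy and in combination with pembrolizumab". Protocol 9.2 has nearly the same text: "all patients enrolled into Phase 1 monotherapy and in combination with pembrolizumab". Both add a condition on treatment received (two doses and a completed Cycle 1, or a DLT in Cycle 1). Neither limits the set to particular parts of the study.

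**Its use.** SAP 7.1.7: "The summary and listing of DLTs will be performed on the DLT-Evaluable Analysis Set".

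**Where DLTs are defined.** Protocol 4.1.2.2.1, for monotherapy: "DLTs during Phase 1a Dose Escalation are defined as any of the following events". Section 4.1.2.2.2 gives the combination criteria under a heading that names the Safety Lead-in. No DLT definition is given for Dose Exploration or Phase 1b.

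**Dose Exploration.** SAP 1.1.2 says that toxicities in these patients "will not be included in the formal DLT calculations per Protocol". Protocol 4.1.3 says the same and refers to Table 5.

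**Grouping.** SAP 3.2 combines Escalation and Exploration patients at the same dose level, and for the other regimen: "safety lead-in in Phase 1a and Phase 1b for combination will be combined for summary". SAP Section 3 makes lead-in plus Phase 1b combination one reporting group, and Phase 1b monotherapy a group of its own. Section 7.1.7 exempts DLT tables from neither rule.

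**Phase limit.** Protocol 9.4.1 says that DLT incidence is to be summarised for Phase 1a.

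**The concern.** A DLT proportion means something only if numerator and denominator come from patients followed under the same DLT rules. As worded, the set adds patients to the denominator who were outside the formal DLT process, and the pooling rule places them in the same column as those who were inside it. DLT incidence is a Phase 1a primary endpoint and is the evidence a reader of the clinical study report would look to for the recommended dose. A programmer following the SAP to the letter would produce a proportion that does not match the patients on whom the Cohort Review Committee decided.

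**Working it through.** **1. Which parts qualify under each statement**

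| Study part | DLTs defined (Protocol 4.1.2.2) | Replaced if not DLT-evaluable (Protocol 7.3) | In the set as worded (SAP 3.1.3) | Pooled with (SAP 3.2, Section 3) |
|---|---|---|---|---|
| 1a Dose Escalation | yes | yes | yes | Exploration at same dose |
| 1a Dose Exploration | no; outside formal DLT calculations | no | yes | Escalation at same dose |
| 1a Combination Safety Lead-in | yes | yes | yes | 1b combination |
| 1b monotherapy | no | no | yes | separate group |
| 1b combination (1bC1) | no | no | yes | Lead-in |

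The second and third columns agree on two parts; the fourth admits all five.

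**2. Planned counts.** The documents give no DLT rate for this set, so the only stated figures to reproduce are the planned numbers: 26 + 22 + 20 = 68 for Phase 1a, 7 × 30 = 210 for Phase 1b, and 68 + 210 = 278 in total. All match SAP 1.3.

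**3. Monotherapy at 20 mg/kg** (the recommended dose, Protocol 4.1.2)

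- Escalation patients: 2 before the data cutoff + 2 after = 4 (Protocol 2.2.5.3).
- DLTs in escalation: 0 (Protocol 2.2.5.4).
- Exploration patients at this dose, cohort 1aE3: up to 10 (Protocol 4.1.3).
- Denominator with Exploration pooled: 4 + 10 = 14, a ratio of 14/4 = 3.5.
- Rate: 0/4 = 0% and 0/14 = 0%, if no DLT is recorded in the added patients.
- Exact one-sided 95% upper bound with zero events, 1 − 0.05^(1/n): n = 4 gives 52.7%; n = 14 gives 19.3%.
- If only 60% of the added patients meet the two-dose condition, n = 4 + 6 = 10, the ratio is 2.5 and the bound is 25.9%.

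**4. Combination at the recommended dose**

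- Lead-in size f: 3, 6 or up to 10 (Protocol 4.1.2.1 and Table 6).
- Cohort 1bC1: up to 30 (Protocol 4.1.4).
- Retention r to a second dose among 1bC1 patients is not stated; assumed 60% to 100%.
- Dilution factor with the number of DLTs held fixed: (f + 30r)/f.

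| Lead-in f | r = 60% | r = 100% |
|---|---|---|
| 3 | 21/3 = 7.0 | 33/3 = 11.0 |
| 6 | 24/6 = 4.0 | 36/6 = 6.0 |
| 10 | 28/10 = 2.8 | 40/10 = 4.0 |

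For one DLT, 1/6 = 16.7% becomes 1/36 = 2.8%, and 1/10 = 10% becomes 1/40 = 2.5%, both at full retention. The row for f = 3 is a limiting case: under Table 6 a DLT among the first 3 leads to 3 more patients at that dose.

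**5. If Phase 1 is a slip for Phase 1a.** Cohort 1bC1 drops out and step 4 no longer applies. Dose Exploration belongs to Phase 1a, so step 3 is unchanged.

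**The case against.** The best defence is that the intent is clear from the rest of the documents. Protocol 9.4.1 confines DLT incidence to Phase 1a, DLTs are endpoints only in Phase 1a, and SAP 1.1.2 sets Exploration aside. On that view Phase 1 is loose wording carried over from Protocol 9.2, and a careful programmer would get it right. The SAP did not remove a limit from the set definition, because the protocol's definition had none.

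Much of this stands for Phase 1b. It does not settle Exploration: correcting the term to Phase 1a keeps those patients in. The exclusion in SAP 1.1.2 sits in the design description, not in the set definition or the DLT analysis section. Because Protocol 4.1.3 ties it to Table 5, it could also be read as covering escalation decisions only.

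Other points stand in full. The SAP plans no confidence interval for DLTs, so the bounds above are illustrations and would not appear in the report. All DLTs are to be listed, with listings sorted by phase and treatment group, so a reader could rebuild the counts.

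Three stronger readings are tempting and are not supported:

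- *The DLT rate at the chosen monotherapy dose is diluted.* No DLT was observed in escalation, so the rate is 0% with either denominator.
- *Up to 90 Phase 1b monotherapy patients dilute the Phase 1a rate.* SAP Section 3 reports them as a separate group.
- *The added patients can never enter the numerator.* Protocol 6.4.4 counts an FPA150 dose reduction during the DLT period as a DLT and does not limit this to Phase 1a. It gives such patients at most a partial DLT rule, but it is a possible route.

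**Conclusion.** The concern holds as a defect in the reporting rule. The set definition and the pooling rule, applied as written, give a DLT denominator that conflicts with where DLTs are defined, with the exclusion of Exploration and with the Phase 1a limit in Protocol 9.4.1.

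- **Monotherapy 20 mg/kg:** denominator 4 to at most 14, rate unchanged at 0%, apparent certainty overstated (upper bound 53% against 19%). This assumes a full cohort 1aE3, all meeting the two-dose condition, no DLT recorded among them, and no escalation patients at this dose beyond the 4 described.
- **Combination:** about 3- to 11-fold dilution, but only if a lead-in DLT occurs, 1bC1 is pooled and no DLT is recorded in 1bC1. The upper end is the limiting case noted above. The documents do not say whether any lead-in DLT occurred.

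A reader might infer that dose selection was affected. It was not: dose decisions follow Tables 5 and 6 and the Cohort Review Committee's review, none of which uses this set. The matter should be corrected because the endpoint is primary in Phase 1a, but it is a reporting issue.

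**What to change.** - In SAP 3.1.3 and Protocol 9.2, restrict the DLT-Evaluable set to patients enrolled in Phase 1a Monotherapy Dose Escalation or the Phase 1a Combination Safety Lead-in.
- In SAP 7.1.7, state that DLTs are summarised by dose level within those two parts only, and that the pooling in SAP 3.2 does not apply to these tables.
- List any DLT-like events in Dose Exploration or Phase 1b separately, labelled by study part, so that no safety information is lost.

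The cost is a few lines of text and one table specification; no new data are needed. The downside is a smaller denominator, and so a less precise DLT summary.

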3.1.4 PK Analysis Set

The PK Analysis Set is defined as all subjects who have received at least one dose of FPA150 and have at least 1 PK sample collected. These subjects will be evaluated for PK analysis unless the number of data points required for analysis is not enough, or significant protocol deviations have affected the data or if key dosing or sample information is missing. The PK Analysis Set is the primary analysis set for all PK analyses.

3.1.5 ADA Analysis Set

The ADA Analysis Set includes all enrolled subjects who received at least 1 dose of FPA150 and have at least 1 ADA sample drawn at any timepoint.

3.2 Subject Grouping

Subjects will be grouped according to the actual treatment they received. Subjects with the same dose level from the dose escalation and exploratory in Phase 1a for monotherapy and safety lead-in in Phase 1a and Phase 1b for combination will be combined for summary.

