This study is designed as a dose escalation, dose exploration, and dose expansion study with objectives that include determination of an MTD and/or RD and assessments of the safety and tolerability of FPA150 alone and in combination with pembrolizumab. The sample size of this study was not determined by statistical considerations. The total number of patients planned for this study is estimated to be up to 278.

Phase 1a will enroll up to 68 patients. The 68 patients include 23 to 26 patients in the Phase 1a Monotherapy Dose Escalation cohorts, 6 to 22 patients in the Phase 1a Combination Safety Lead-in and up to 20 additional patients in the Phase 1a Dose Exploration (10 patients with B7-H4 high and 10 patients with low/no B7-H4 expression; refer to Section 4.1.3) to further evaluate safety, PK, pharmacodynamics, and clinical activity at one or more dose levels (to be conditional upon the dose level clearing DLT criteria).

For the objective of estimating the overall response rate (ORR) of FPA150 in Phase 1b Dose Expansion, it is estimated that up to 30 patients will be enrolled to ensure 25 evaluable patients in each cohort. The following table displays the corresponding 2-sided 90% confidence interval (CI) and the precision for the various observed response rates based on 25 evaluable patients. The sample size of 25 is chosen to ensure that it will allow to exclude 10% when the observed ORR is 24% or higher.

Phase 1b will enroll up to 210 patients with specific tumor types. Up to 30 patients are planned for each of three FPA150 Monotherapy expansion cohorts and the one FPA150 in combination with pembrolizumab cohort. Additional cohorts of up to 30 patients each may be enrolled (not to exceed 7 cohorts), based on emerging clinical and translational data.

Two-Sided 90% Confidence Intervals of the Observed Response Rates

Sample Size	Observed Response Rate	90% CI	Precision (longest one-sided CI length*)
25	5/25 (20%)	(8%, 38%)	18%
	6/25 (24%)	(11%, 42%)	18%
	7/25 (28%)	(14%, 46%)	18%
	8/25 (32%)	(17%, 50%)	18%
	9/25 (36%)	(20%, 54%)	18%
	10/25 (40%)	(24%, 58%)	18%

Abbreviations: CI = confidence interval.

*Distance from the observed response rate to the lower or upper CI boundary.

Safety Analysis:

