4.1.3 Study Design: Phase 1a Dose Exploration

Phase 1a includes a dose exploration cohort that may enroll beyond 3 patients (up to 20 additional patients across all dose levels). This 20 patients include 10 patients whose tumors express high levels of B7-H4 protein (3 mg and 10 mg), to further evaluate safety, PK, pharmacodynamics, and clinical activity at that dose (to be conditional upon the dose level clearing DLT criteria) of FPA150 monotherapy. It also includes up to 10 patients selected to have varying levels of B7-H4 expression [REDACTED] dosed at the FPA150 monotherapy MTD/RD.

Table 7: Proposed Dose Cohort/Level for Phase 1a Dose Exploration

Cohort	Dose/Regimen	B7-H4 Status
1aE1	FPA150 3 mg/kg	High
1aE2	FPA150 10mg/kg	High
1aE3	FPA150 monotherapy MTD/RD	

Abbreviations: MTD = maximum tolerated dose; Q3W = once every 3 weeks; RD = recommended dose

Toxicities observed in these patients will contribute to the overall assessment of safety and tolerability, but will not be included in the formal DLT calculations per Protocol [Table 5](#).

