4.5 Scientific Rationale for Study Design

This is a Phase 1a/1b study. Phase 1a includes an accelerated titration design followed by standard 3+3 dose escalation design in unselected solid tumor patients. Once MTD/RD of FPA150 monotherapy is identified a cohort of patients will be enrolled on a Phase 1a Safety Lead-in with FPA150 + pembrolizumab to determine the RD of FPA150 in the combination.

Phase 1a will also include the option of enrolling up to 20 additional patients at 1 or more dose levels with varying levels of B7-H4 expression. Fresh biopsies will be mandatory in these additional patients. This will enable a more robust exploration of safety, PK and pharmacodynamics at any dose level.

Phase 1b is a dose expansion portion in patients with advanced breast, ovarian, and endometrial cancer that will be selected based on B7-H4 expression. These tumor types have been identified based on their known high prevalence of B7-H4 expression (Section 2.1) and limited availability of effective therapies in the unresectable and metastatic setting. Based on the preclinical activity of FPA150 and PD-L1 inhibitors (see Section 2.2.2.2) Phase 1b will also include a cohort of the combination of FPA150 and pembrolizumab to evaluate safety, tolerability and preliminary efficacy. The initial tumor type to be evaluated with the combination will be ovarian cancer based on the high unmet need in this population, high expression of B7-H4 and the limited clinical benefit observed with anti-PD1 agents alone. Additional cohorts with different tumor types or combinations may be enrolled based on emerging clinical and translational data for this pathway and molecule. Phase 1b Dose Expansion will enable a more thorough investigation of the clinical and biological activity of FPA150 monotherapy and in combination with pembrolizumab in more homogenous patient groups (by tumor type and biomarker expression) and will help define further clinical development of this molecule.

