4.7 Patient Selection

FPA150 is an antibody designed to recognize B7-H4 which is expressed highly on tumors, such as on breast cancer, ovarian cancer, and endometrial cancer. Because it is predicted that patients whose tumors have higher expression of the target B7-H4 protein are more likely to respond to FPA150, patients will undergo pre-screening to allow selection based on B7-H4 expression in the Phase 1a Combination Safety Lead-in, Phase 1a Monotherapy Dose Exploration and in Phase 1b Dose Expansion (Monotherapy and in combination with pembrolizumab).

Tumor samples (fresh or archival) from all patients will be assessed by IHC to determine the expression of B7-H4 protein, and patients in Phase 1b and a subset of patients in Phase 1a will be selected based on being positive for B7-H4.

5 Study Population

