8.11 Predictive and Pharmacodynamic Biomarkers

Samples for predictive and pharmacodynamic biomarker assessment will be collected and processed according to instructions provided in a separate laboratory manual. Additional guidance for sampling and procedures is provided in the following appendices:

- Specific timing requirements for study assessments and procedures: [Appendix 1](#) Schedule of Assessments.
- Guidance for the specific timing of PK, immunogenicity, and pharmacodynamic sample collection: [Appendix 2](#) Schedule of Pharmacokinetic, Immunogenicity, and Pharmacodynamic Blood Sample Collection.
- Specific pharmacodynamic analyses to be conducted: [Appendix 3](#) List of Pharmacodynamic Samples for Analyses.

A variety of endpoints that could monitor drug activity and potentially predict clinical response to FPA150 may be investigated in peripheral blood and archival and/or fresh tumor specimens, collected from patients prior to and during treatment. Data from these analyses will be evaluated for association with response and/or safety data.

Exploratory biomarker analysis will be conducted to investigate the relationship between baseline target levels, tumor immune phenotype, pharmacodynamic response within the tumor and in the periphery, and efficacy.

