3.3 Examination of Subject Subgroups

There are no prespecified subject subgroupings for efficacy and safety analyses.

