5.2 Other Baseline Disease Characteristics

Other baseline characteristics include baseline ECOG PS and B7-H4 expression level by IHC. Summary of ECOG PS by treatment group for the Safety Analysis Set will be provided as part of the disease-specific baseline characteristics. A by-subject listing will be provided for B7-H4 expression level by IHC.

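### Phase 1a monotherapy response rates pool B7-H4-selected with unselected patients by dose, and no response rate by B7-H4 expression level is planned

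*SAP*

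**What the plan says.** **Selection hypothesis.** Protocol 4.7 selects patients on expression "Because it is predicted that patients whose tumors have higher expression of the target B7-H4 protein are more likely to respond to FPA150". It also says that tumors from all patients will be tested by IHC.

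**Phase 1a cohorts.** Protocol 4.5 describes the escalation part: "Phase 1a includes an accelerated titration design followed by standard 3+3 dose escalation design in unselected solid tumor patients". Dose Exploration is defined by expression. Protocol 4.1.3 states: "This 20 patients include 10 patients whose tumors express high levels of B7-H4 protein (3 mg and 10 mg"), followed by up to 10 patients with varying expression at the MTD/RD. The sample-size text in the synopsis splits the same 20 as "10 patients with B7-H4 high and 10 patients with low/no B7-H4 expression". The RD is 20 mg/kg (Protocol 4.1.2, SAP 1.1.1), so 1aE1, 1aE2 and 1aE3 all sit on doses also used in escalation.

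**Protocol analysis.** Protocol 9.4.2 gives ORR by dose/cohort. Protocol 8.11 says of the biomarker work: "Data from these analyses will be evaluated for association with response and/or safety data". It also says that the relation of baseline target levels to efficacy will be investigated.

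**SAP analysis.** Section 3 makes Escalation plus Exploration one reporting group, and 3.2 merges "Subjects with the same dose level from the dose escalation and exploratory in Phase 1a for monotherapy". Section 3.3 reads: "There are no prespecified subject subgroupings for efficacy and safety analyses". Section 5.2 summarises ECOG status, but for B7-H4: "A by-subject listing will be provided for B7-H4 expression level by IHC". Section 6.1 gives ORR by treatment group. Section 6.3, on changes from the protocol's efficacy analysis, names only duration of response and PFS.

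**The concern.** Expression is the variable on which this program selects patients, and the Exploration cohorts were filled according to it. Once they are merged with escalation patients at the same dose, the Phase 1a table has one row per dose with a different expression mix in each. Patients known to be high are added at 3 and 10 mg/kg; patients of varying or low expression are added at 20 mg/kg. If the selection hypothesis is right, the pooled table could show response falling at the top dose when the drug effect is the same throughout.

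The second loss is that no table relates response to expression level. That relation can then be examined only by working from listings, with categories chosen after responses are known.

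**Working it through.** **1. The plan's own response rates.** SAP 1.3 uses 5% (futility) and 20% (efficacy) and states a 0.81 probability of stopping with at most 1 response in 16. Check: 0.95^16 + 16 × 0.05 × 0.95^15 = 0.440 + 0.371 = 0.811. This reproduces. I borrow the two rates below; the documents do not attach them to expression levels.

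**2. Patients in each pool.**
- Exploration, high expression: 10 in total over 3 and 10 mg/kg (Protocol 4.1.3). I assume 5 at each. Protocol 2.2.5.3 reports 5 at 3 mg/kg and 1 at 10 mg/kg by the December 2018 cut-off.
- Exploration at the RD: up to 10. I first assume all low/no, as the synopsis says, and relax this in step 4.
- Escalation: n = 3 or 6 per dose, from the 3+3 rule. Protocol 2.2.5.3 gives 4 at 20 mg/kg; the count at 3 mg/kg is not stated.
- Share f of unselected patients who are high: not stated, so 10% to 90%.

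**3. Pooled ORR with no dose effect.** Let u = 0.20f + 0.05(1 − f).
- 3 or 10 mg/kg: (5 × 0.20 + n × u)/(5 + n)
- RD: (10 × 0.05 + n × u)/(10 + n)

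| f | n | 3 or 10 mg/kg | RD |
|---|---|---|---|
| 10% | 3 | 14.9% | 5.3% |
| 10% | 6 | 12.6% | 5.6% |
| 50% | 3 | 17.2% | 6.7% |
| 50% | 6 | 15.9% | 7.8% |
| 90% | 3 | 19.4% | 8.1% |
| 90% | 6 | 19.2% | 10.1% |

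Example (f = 10%, n = 6): u = 0.065; (1.00 + 0.39)/11 = 12.6%; (0.50 + 0.39)/16 = 5.6%. Within a row, the gap is about 7 to 11 percentage points and comes from expression mix alone. The high-expression share is 51% to 96% at 3 or 10 mg/kg and 2% to 34% at the RD.

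**4. If half of 1aE3 were high.** The RD numerator becomes 10 × 0.125 + n × u.
- f = 10%, n = 6: (1.25 + 0.39)/16 = 10.3%, against 12.6%.
- f = 90%, n = 3: (1.25 + 0.555)/13 = 13.9%, against 19.4%.

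The gap shrinks to roughly 2 to 6 points but keeps its direction.

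**5. Precision after a split.** Exact 95% intervals (the method in SAP 6.1) for a group of 10: 0/10 gives 0% to 31%; 1/10, 0.3% to 45%; 2/10, 2.5% to 56%; 3/10, 7% to 65%. Separate rows describe; they do not test.

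**6. A related mismatch.** The synopsis plans low/no expressers in Exploration, while Protocol 5.4 classes B7-H4-negative Exploration patients as pre-screen failures. The two need reconciling, because they determine who is in 1aE3.

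**The case against.** **What stands.**
- The stated purpose of Exploration is safety, PK, pharmacodynamics and clinical activity at a dose. Comparing response by expression is not its declared question, and pooling by dose is consistent with that purpose.
- Protocol 9.4.2 contains no ORR by B7-H4, and its dose/cohort wording leaves latitude. The target-level analysis sits in 8.11 as exploratory work, so the sponsor can argue that SAP 6.3 need not mention it.
- Phase 1a efficacy is exploratory, no formal testing is planned, and the RD was fixed by January 2019, before the September 2021 SAP. No dose decision depends on these tables.
- Exploration has at most 20 patients, and the listings of expression, response and enrolled group would let a reader rebuild the rates.

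These points limit the consequence without removing the gap. A listing is not the evaluation that 8.11 describes, and neither document refers to a separate biomarker report.

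**Stronger readings that a reader might infer, and why they fail.**
- *No ORR in B7-H4-selected patients is produced.* Phase 1b monotherapy is reported separately and requires B7-H4 positivity, and the combination group is positive throughout. Mixing is confined to Phase 1a monotherapy.
- *The SAP forbids subgroups.* It says that none are prespecified.
- *Pooling caps the observed rate at a known figure.* Suppose 20% response in high and 0% in others, with 5 high and 3 unselected patients at 3 mg/kg. If k of the 3 are high, the pooled rate is (5 + k) × 0.20/8, or 12.5% to 20%. Unselected does not mean low: 9 of the first 24 patients had ovarian cancer, which the protocol describes as high-expressing.

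**Conclusion.** The point holds for Phase 1a monotherapy. Followed as written, the SAP gives per-dose response rates in which dose and B7-H4 mix are confounded, and it plans no response rate by expression level in any part of the study. The protocol's dose/cohort presentation and its target-level analysis are not carried through, and the SAP does not say so.

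The 12.6% to 19.4% against 5.3% to 10.1% contrast is an illustration, not an estimate. It rests on assumed rates of 20% and 5%, no dose effect, 5 high expressers at each of the two lower doses, 10 low/no expressers at the RD, and the stated ranges for n and f. A more mixed 1aE3 narrows the contrast; the cohort table's entry for its B7-H4 status is redacted, which is not a fault of the plan. The consequence is for interpretation of exploratory results. The documents do not support a claim that the RD or the Phase 1b ORR is biased by this.

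**What to change.** 1. **SAP 3.2 and 6.1:** show 1aE1, 1aE2 and 1aE3 as separate columns beside the escalation patients at the same dose. A pooled column may be kept as an extra.
2. **SAP 3.3 and 6.1:** add one descriptive table of ORR by central-IHC B7-H4 category with exact intervals. Restrict it to Phase 1a monotherapy patients at 3, 10 and 20 mg/kg and show it by dose. Show Phase 1b separately by tumor cohort. Do not pool all monotherapy patients: that would mix low escalation doses in any solid tumor with B7-H4-positive breast, ovarian and endometrial patients at the RD, confounding expression with dose and tumor type. Fix the IHC categories before the table is run.
3. **SAP 5.2:** summarise B7-H4 in the baseline table as well as listing it.
4. **SAP 6.3:** record and justify any part that is dropped. If analyses relating biomarkers to response will be reported elsewhere, say where.
5. **Protocol synopsis and Section 5.4:** reconcile the status of low/no expressers in Exploration.

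Items 1 to 4 need SAP wording and a few table changes using data already planned for collection. The downside is wide intervals, so the tables must be labelled descriptive.
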